### **Treatment Compliance**

Patient compliance will be reported by patient interview to assure no medications were missed. The DOAC bottle will be returned to the study coordinator at their 1 month follow up visit.

Final revised protocol

## STUDY ASSESSMENTS AND PROCEDURES

### Study Schematic

#### Time and Events Schedule

Procedure	Baseline (Within 30 days of the procedure)	Randomization (Within 48 prior to procedure)	Prior to Procedure (Within 24 hours of procedure)	Day of Procedure	24-48 hours Post- Procedure	Discharge	Day 30 (+/- 7 days) Follow- Up
Eligibility Assessments							
Informed Consent	X						
Medical History	X						
Inclusion/Exclusion Criteria	X						
Study Assessments:							
Physical Examination	X			X	X	X	X
Vital Signs	X		X	X	X	X	X
Adverse Events Assessment	X	X	X	X	X	X	X
Evaluation of Bleeding Events	X		X	X	X	X	X
Laboratory Tests	X						
Pregnancy Test	X						
Ablation Procedure				X			
Device Interrogation			X		X	X	X
Cerebral MRI					X		X
Neurology Evaluation NIHSS			X		X		X
EQ5D Survey			X		X		X
Randomization		X					
Dispense Study Drug				X (3 hours post hemostasis)			
Drug Compliance			X	X	X	X	X

## Schedule of Events

### Baseline (to be completed within 30 days prior to the procedure)

- Informed Consent
- Medical History including medication review
- Inclusion/Exclusion Criteria reviewed
- Physical Exam
- Vital Signs
- Adverse Event Assessment
- Evaluation of Bleeding events – including TIMI evaluation
- Laboratory tests (including Chemistry, CBC, Pregnancy Test)
- Pregnancy Test (if applicable)

### Randomization

- Adverse Event Assessment
- Randomization

### Prior to Procedure (within 24 hours of procedure)

- Vital Signs
- Adverse Event Assessment
- Evaluation of Bleeding events – including TIMI evaluation
- Device Interrogation
- Neurology Evaluation – NIHSS
- EQ5D Survey

### Day of Procedure

- Physical Exam
- Vital Signs
- Adverse Event Assessment
- Dispense Study Drug
- Evaluation of Bleeding events – including TIMI evaluation
- Ablation Procedure

Post Procedure (within 24-48 hours)

- Physical Exam
- Vital Signs
- Adverse Event Assessment
- Evaluation of Bleeding events – including TIMI evaluation
- Device Interrogation
- Cerebral MRI
- Neurology Evaluation – NIHSS
- EQ5D Survey

Discharge

- Physical Exam
- Vital Signs
- Adverse Event Assessment
- Evaluation of Bleeding events – including TIMI evaluation Device Interrogation

Day 30 Follow up (+/- 7 days)

- Physical Exam
- Vital Signs
- Adverse Event Assessment
- Evaluation of Bleeding events – including TIMI evaluation
- Device Interrogation
- Cerebral MRI
- Neurology Evaluation – NIHSS
- EQ5D Survey

**Safety Assessments**

**STROKE VT**

**Non-CABG Surgery Related Bleeding Events Criteria**

TIMI Major Bleeding Events
 
Any Symptomatic Intracranial Hemorrhage, or clinically overt signs of hemorrhage (including imaging) associated with a drop in hemoglobin of >5 g/dL (or when the hemoglobin concentration is not available, an absolute drop in hematocrit of >15% or Fatal Bleeding (bleeding that directly results in death within 7 days post procedure)

TIMI Minor Bleeding Events
 
Any clinically overt sign of hemorrhage (including imaging) that is associated with a fall in hemoglobin concentration of 3 to < 5 g/dL (or, when hemoglobin concentration is not available, an absolute drop in hematocrit of 9 to < 15%)

TIMI Bleeding Events Requiring Medical Attention
 
Any bleeding event that requires medical treatment, surgical treatment, or laboratory evaluation and does not meet criteria for a major or minor bleeding event, as defined above

Insignificant Bleeding Events (ie, TIMI Minimal Bleeding Event)
 
A reported blood loss or bleeding event episode not meeting any of the above criteria

Clinically Significant Bleeding Events
 
The composite endpoint of TIMI major bleeding event, TIMI minor bleeding event, or bleeding event requiring medical attention is considered clinically significant for the TIMI scale

Not a TIMI Bleeding Event

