### Primary End Point Assessment

Incidence of periprocedural embolic events –TIA/CVA/other systemic embolic events immediately after the left ventricular arrhythmia ablation up to 30 days post left ventricular arrhythmia ablation.

The incidence of new asymptomatic cerebrovascular events as documented by MRI at 24-48 hours post procedure and at 30 days after the left ventricular arrhythmia ablation.

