### **DATA MONITORING COMMITTEE**

To meet the study's ethical responsibility to its subjects, an independent data safety monitoring Board (DSMB) will monitor results during the study. The board consists of 2 physicians and 1 statistician who have no formal involvement or conflict of interest with the subjects or the investigators. Records will be reviewed after the first 50 patients and then at the completion of the study.

If the major bleeding events in the DOAC group occur at >15% but <30% (absolute event rate) of those in the ASA group during any of the assessments, a recommendation will be made to consider modifying the study by the members of the DSMB. First consideration to modify is to decrease the dose of the drug to 2.5mg PO twice daily. If the major bleeding events in the DOAC group occur at >30% (absolute event rate) of those in the ASA group during any of the assessments, a recommendation will be made to stop the study by the members of the DSMB.

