#### **Data Collection Center**

The Kansas City Heart Rhythm Research Foundation will be the coordinating site for the study. A project manager (PM) with the help of the PI will create the study worksheets and create the CRFs. The sites will complete the paper CRF and submit via secure email to the project manager. The PM will assist the Database Manager (DM) with updating the access database and providing computer support for outside centers. All data will be submitted via secure email including de-identified patient data that is to be used as source.

Participant's data will be de-identified and a code will be assigned. The code will consist of Site Number, Patient Number and Patient Initials. The coordinator at that site will have access to the code; the linking list will be destroyed at the completion of the project.

**Statistical analysis:** Patients will be randomized in a stratified manner to control arm versus treatment arm. We will analyze the differences in secondary endpoints between the two groups for major, minor bleeding and cardiovascular mortality up to 30 days post ablation. Categorical variables will be reported as counts and percentages and continuous variables will be expressed as mean  $\pm$  SD. Continuous variables will be compared using t-test for normally distributed data or Mann Whitney U test for non-normally distributed data as deemed appropriate. Categorical events will be compared using chi-square test for parametric data.

Univariate and multi-variate analysis will be performed to identify the predictors of systemic thromboembolic events and mortality. This is a pilot study to study the feasibility and safety of the study. A larger study will be done in the future if there is a positive signal.

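### The protocol defines a clinically significant bleeding composite but leaves it out of the between-arm comparison, so treated bleeds with a hemoglobin fall below 3 g/dL appear only among general adverse events

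*Combined protocol and SAP*

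**What the plan says.** The table under Safety Assessments (Non-CABG Surgery Related Bleeding Events Criteria) sets out the bleeding classes.

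- Major: "Any Symptomatic Intracranial Hemorrhage, or clinically overt signs of hemorrhage (including imaging) associated with a drop in hemoglobin of" more than 5 g/dL, or a bleed fatal within 7 days of the procedure.
- Minor: an overt bleed "that is associated with a fall in hemoglobin concentration of 3 to" below 5 g/dL. Both classes have hematocrit equivalents.
- Requiring medical attention, the third class: "Any bleeding event that requires medical treatment, surgical treatment, or laboratory evaluation and does not meet criteria for a major or minor bleeding event".
- Insignificant (TIMI minimal): any reported bleed outside the classes above.

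The table then adds: "The composite endpoint of TIMI major bleeding event, TIMI minor bleeding event, or bleeding event requiring medical attention is considered clinically significant".

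The Secondary Objectives name major and minor bleeding. Secondary End Point Assessments lists these as items A and B, the two mortality endpoints as C and D, and all other adverse events as E. The statistical analysis paragraph, under Data Collection Center, says differences in secondary endpoints will be analyzed "for major, minor bleeding and cardiovascular mortality up to 30 days post ablation". The Data Monitoring Committee section attaches its numeric thresholds to major bleeding alone: "If the major bleeding events in the DOAC group occur at" the stated rates.

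On the ischemic side, the Primary End Point Assessment includes "The incidence of new asymptomatic cerebrovascular events as documented by MRI at 24-48 hours post procedure" and again at 30 days.

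**The concern.** The protocol calls clinically significant bleeding a composite endpoint and schedules a TIMI evaluation at six of its seven visits (all but randomization). No objective, listed endpoint or analysis then uses the composite. An access-site repair or a drained pericardial bleed with a fall below 3 g/dL would normally be regarded as a bleeding complication of an anticoagulant strategy. Here it would not enter either bleeding endpoint.

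This bears on the pilot's purpose. The introduction expects DOAC to anticoagulate without more bleeding complications. The analysis paragraph gives feasibility and safety as the aim, with a larger trial to follow a positive signal. A bleeding comparison limited to the two classes with a hemoglobin requirement could look clean while treated bleeds differ between arms.

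Two features sharpen the concern. First, the Time and Events Schedule places laboratory tests, including the CBC, at baseline only. The two analyzed classes therefore depend largely on a fall with no scheduled post-procedure value, whereas the unused class needs no such fall. Second, the brain MRIs are read in one direction only. A silent infarct counts toward the primary endpoint, and no reading for silent hemorrhage is specified.

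**Working it through.** The plan gives no bleeding rate or bleeding calculation to reproduce. The check is therefore a trace of each type of bleed through the definitions, followed by an illustration of the size.

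**Trace** (fall = hemoglobin fall, with the hematocrit equivalent where hemoglobin is missing)

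| Bleed | Class | In planned major/minor comparison | In composite |
|---|---|---|---|
| Symptomatic intracranial, or fatal within 7 days | Major | Yes | Yes |
| Overt, fall above 5 g/dL | Major | Yes | Yes |
| Overt, fall 3 to below 5 g/dL | Minor | Yes | Yes |
| Treated or sent for laboratory evaluation, non-fatal, fall below 3 g/dL | Requiring medical attention | No | Yes |
| Silent intracranial, fall below 3 g/dL, treated or sent for laboratory evaluation | Requiring medical attention | No | Yes |
| Silent intracranial, fall below 3 g/dL, neither | Insignificant | No | No |

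The fourth and fifth rows are the gap that the composite closes. The last row stays open even with the composite. The primary endpoint does not pick it up either: Cerebral MRI defines an acute embolic lesion, and Neurology Evaluations defines a silent event as an infarct.

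**Arm size.** 52 enrolled − 2 for attrition = 50 analyzed; 50 / 2 = 25 per arm.

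**Illustration.** Suppose four DOAC patients and no ASA patient have surgically treated, non-fatal bleeds with a fall of 2.5 g/dL.

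- Planned comparison: 0/25 vs 0/25 for major and for minor. Exact 95% upper limit for 0/25 = 1 − 0.025^(1/25) = 13.7%.
- Composite: 4/25 = 16.0% (exact 95% interval 4.5% to 36.1%) vs 0/25.
- Fisher's exact p = 0.110. Uncorrected chi-square = 50 × (4 × 25 − 21 × 0)² / (25 × 25 × 4 × 46) = 500,000 / 115,000 = 4.35, p = 0.037. The two tests disagree because only two events are expected per arm, which is a reason to report exact intervals.

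**How much could be missed (assumed rates; none is in the documents).**

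- Major bleeding at 2% to 5% in both arms: the chance of no major bleed in 50 patients is 0.98^50 = 36% to 0.95^50 = 8%.
- Treated bleeds with a fall below 3 g/dL at 10% to 20% on DOAC and 3% to 5% on ASA: 25 × 0.10 = 2.5 to 25 × 0.20 = 5 DOAC patients, and 25 × 0.03 = 0.75 to 25 × 0.05 = 1.25 ASA patients, would sit outside the comparison.

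**What the composite could show.** At 25 per arm and two-sided 0.05, power for 10% vs 15% is about 3% by Fisher's exact test and 9% by uncorrected chi-square. For 5% vs 20% it is about 20% and 38%.

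**The case against.** The best defense is that nothing disappears. A treated bleed is an adverse event under item E of the secondary endpoints. If it prolongs hospitalization or needs intervention to prevent a serious outcome, it is an SAE, collected and reported within 24 hours. The DSMB and steering committee adjudicate disagreements, and the DSMB reviews records as well as the major-bleeding rate. All of this stands. A reader might infer that these bleeds vanish from the trial or are hidden from the DSMB, and the documents do not support that. The bleeds do miss a standardized comparison of bleeding by arm. Adverse-event reporting is a weak substitute, because the protocol tells staff not to ask about specific events and begins non-serious collection only at study-drug initiation.

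The analysis paragraph may not be a closed list, since it also omits all-cause mortality. That is fair, but the objectives and endpoints A and B leave the composite out as well.

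Using the top two tiers of a named scale is a legitimate choice in a pilot. This also stands, and it is why the point is an improvement and not an error in the scale.

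A reader might infer that the composite would also capture silent intracranial bleeds in general. It would not: an untreated, uninvestigated one is classed as insignificant. Nor do the documents show that the scans would find such bleeds reliably. The listed sequences are T1, FLAIR and DWI, lesion reading is described only for emboli, and there is no baseline scan.

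Finally, the first DSMB review follows 50 of the 52 patients, so a fuller DSMB table could protect few participants. That stands too.

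**Conclusion.** The concern holds as a gap between a defined endpoint and the planned analysis. Treated bleeds with a hemoglobin fall below 3 g/dL contribute nothing to the major/minor comparison however many occur, unless they are fatal within 7 days or a symptomatic intracranial hemorrhage. In the illustration the discrepancy is 0/25 against 4/25. The trace rests only on the protocol's text; the likely number of such events rests on assumed rates.

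The MRI asymmetry is real but narrower. Silent ischemia counts in the primary endpoint and silent hemorrhage has no planned reading, yet no rate of silent hemorrhage is given and the scans' ability to show it is not established.

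The documents do not support a claim that the trial would miss a safety signal altogether, or that the composite would give a powered bleeding test. The change is worth making because safety is a stated aim and the data are already to be collected. The gain is mainly descriptive.

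**What to change.** 1. Add clinically significant bleeding, as already defined, to Secondary End Point Assessments.
2. Add it to the between-arm comparison in the statistical analysis paragraph. Report counts, percentages and exact confidence intervals by arm, with the three component classes shown separately, because the third class also admits bleeds that led only to a laboratory test.
3. Include the same table in the DSMB material, leaving the existing trigger unchanged.
4. Have the existing blinded radiologist record any intracranial hemorrhage seen on the two scheduled MRIs, whatever the symptoms or hemoglobin change. Tabulate it by arm beside the silent ischemic lesions as descriptive data. State that there is no baseline scan and that the listed sequences are described only for embolic lesions.

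The cost is protocol wording, one more table and one field on the MRI reading form; no visit or scan is added. The reported bleeding profile may look slightly less favorable. With 25 per arm, a null result on the composite should not be read as evidence of equal bleeding.

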### Secondary End Point Assessments

- A. Major bleeding events as defined above using TIMI criteria
- B. Minor Bleeding events as defined by the TIMI criteria

- C. Cardiovascular mortality
- D. All-Cause mortality
- E. Any other adverse events occurring during the study period

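### The fatal-bleeding criterion for a TIMI major bleed stops at 7 days although treatment and the bleeding comparison run to 30, and the drop-based grades have no scheduled hemoglobin after baseline

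*Combined protocol and SAP*

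**What the plan says.** All places are in the combined protocol and SAP.

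- **Bleeding criteria table (Safety Assessments).** A bleed is TIMI major if it meets any one of three criteria: symptomatic intracranial hemorrhage; overt bleeding with a hemoglobin drop above 5 g/dL (hematocrit above 15% if hemoglobin is unavailable); or "Fatal Bleeding (bleeding that directly results in death within 7 days post procedure". A minor bleed is an overt one "that is associated with a fall in hemoglobin concentration of 3 to" less than 5 g/dL, or 9 to less than 15% by hematocrit. Below these come a medical-attention class and an insignificant class. The table also defines a composite: major, minor, "or bleeding event requiring medical attention is considered clinically significant for the TIMI scale".
- **Study Design and Duration.** Assigned drugs continue for at least 30 days after ablation.
- **Secondary Objectives and Statistical analysis.** Bleeding is assessed up to 30 days, and the arms are compared for "major, minor bleeding and cardiovascular mortality up to 30 days post ablation". Secondary endpoint A is "Major bleeding events as defined above using TIMI criteria".
- **Glossary.** Peri-procedural bleeding, the term used in the Secondary Objectives, is limited to 48 hours either side of the procedure.
- **Schedule of Events.** "Evaluation of Bleeding events – including TIMI evaluation" is listed on the day of procedure, at 24-48 hours, at discharge and at day 30. Blood work, "Laboratory tests (including Chemistry, CBC, Pregnancy Test", is listed at baseline only, which may be up to 30 days before the procedure.
- **Data Monitoring Committee.** The modify/stop rule begins "If the major bleeding events in the DOAC group occur at" and sets limits of 15% and 30%. It does not name TIMI. Records are reviewed after 50 patients and at completion.

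**The concern.** The time limit on the fatal criterion runs from the procedure, not from the bleed, and is shorter than both the exposure and the endpoint window. Followed as written, the table can place a bleed that killed the patient in the minor class or lower. Major and minor bleeding are the first two secondary endpoints of a pilot meant to study feasibility and safety, and a larger trial depends on a positive signal.

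The hemoglobin schedule adds to this. A late fatal bleed outside the brain can be graded major only through a measured drop, and no measurement is planned after baseline. The table also does not say from which value a drop is counted. Whether a bleed can be graded then depends on who happened to be tested, by staff who may know the treatment.

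**Working it through.** The plan states no figure that depends on these definitions, so there is none to reproduce. The check applies the printed criteria to cases and then sizes what can be sized.

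**1. Fatal bleeds under the printed criteria**

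| Bleed | Recorded hemoglobin drop | Death | Grade as printed |
|---|---|---|---|
| Extracranial | 4 g/dL | day 7 | major (fatal criterion) |
| Extracranial | 4 g/dL | day 9 | minor |
| Extracranial | none recorded | day 9 | medical attention if treated or investigated, otherwise insignificant |
| Extracranial | 5.1 g/dL | day 9 | major (drop criterion) |
| Symptomatic intracranial | any | day 9 | major (intracranial criterion) |

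The gap is the second and third rows: late, extracranial, and without a qualifying recorded drop.

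**2. Days outside the fatal criterion**

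30 − 7 = 23 days; 23/30 = 77%. This is a share of calendar days, not of events. The documents give no bleeding rate or timing from which to derive a share of events.

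**3. The boundary**

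A drop of 4.9 g/dL is minor, 5.0 is neither, and 5.1 is major; the hematocrit limits behave the same way at 15%. A 5.0 g/dL bleed thus ranks below a 4.9 g/dL bleed. A greater-or-equal sign may have been lost in the printed table, so the source scale should be checked first.

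**4. Hemoglobin against grading visits**

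In the Time and Events Schedule, bleeding is evaluated at 6 points: baseline, before the procedure, day of procedure, 24-48 hours, discharge and day 30. Laboratory tests are ticked at 1 of the 6, baseline. For a bleed on day 30, the only scheduled value can be 30 + 30 = 60 days old. The hematocrit alternative needs the same blood count.

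**5. What one event can do to the DSMB rule**

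Assumptions: the rule uses the TIMI definition; its limits are percentage points over aspirin; 25 patients per arm; no major bleeds on aspirin.

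- One event = 1/25 = 4 percentage points.
- 15% limit: 0.15 × 25 = 3.75, so 3/25 (12%) is below and 4/25 (16%) is above.
- 30% limit: 0.30 × 25 = 7.5, so 7/25 (28%) is below and 8/25 (32%) is above.

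One reclassified bleed changes the result only if the DOAC count sits exactly at a limit. The first review comes after 50 of 52 patients (50/52 = 96%), so little of the trial remains to be altered.

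**The case against.** Five points can be made on the other side.

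- **The three major criteria are alternatives.** A reader might infer that every fatal bleed after day 7 drops out of the major count. The table does not support that: a late fatal intracranial bleed, or one with a recorded drop above the limit, is still major. This stands and narrows the gap to the two rows shown in the working.
- **The deaths are not lost.** They count in all-cause mortality, and SAEs are collected to 30 days after dosing ends and reported within 24 hours. This also stands. Cardiovascular mortality is undefined, so only all-cause mortality is certain to include them, and neither mortality endpoint identifies a death as due to bleeding.
- **The 30-day window is itself contradicted.** On the glossary's 48-hour definition, a 7-day limit is not short. The objectives and the analysis text both say 30 days, which favors that reading, but the conflict is real and the 23-day figure depends on how it is resolved.
- **No scheduled test does not mean no test.** Drop-based grades require overt bleeding, which usually prompts a blood count, and the plan captures clinically significant laboratory results. A reader might infer that bleeds go ungraded, or that one arm is favored. The documents establish neither; they do not say what is routine after ablation.
- **The DSMB effect is limited.** A reader might infer that the modify/stop rule is compromised. The rule does not cite TIMI, although the bleeding table is the only definition of major bleeding available. It is first applied when enrollment is nearly complete, and the DSMB would also see fatal events through SAE handling.

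**Conclusion.** The mismatch is real and should be corrected, but its expected effect is small. If the 30-day window in the objectives and analysis text is the intended one, the fatal criterion is silent on 23 of 30 days, and a late extracranial fatal bleed without a qualifying recorded drop is graded minor or lower. How many bleeds this touches cannot be estimated from the documents; in a 50-patient analysis it is probably few, perhaps none.

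The boundary gap holds for the text as printed, subject to a check of the source scale. The hemoglobin point is a risk of incomplete or uneven grading, of unknown size and direction. Any effect on the DSMB rule needs the assumptions in step 5 of the working and would fall on near-final reviews.

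**What to change.** 1. **Fatal bleeding.** Either count as major any bleed that directly results in death through day 30 and label the scale as modified TIMI, or keep the scale as printed and report fatal bleeding through day 30 by arm on its own line. The SAE record already supplies the data.
2. **Boundary.** After checking the source scale, word the limits so that a drop of exactly 5 g/dL or 15% falls in one grade.
3. **Hemoglobin.** For every overt bleed through day 30, record on the CRF the hemoglobin or hematocrit obtained, in the same way in both arms, and name one pre-procedure value as the reference. No added blood count is needed. One at 24-48 hours would come after most procedural bleeds. If used as the reference for later bleeds, it could already be lowered by procedural loss and so shrink the measured drop.
4. **Window.** Reconcile the glossary's 48-hour definition with the 30-day window in the Secondary Objectives and Statistical analysis.

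Items 1, 2 and 4 are wording changes; item 3 adds a CRF field. There are two downsides. The recorded major-bleed count may be slightly higher, so the DSMB should be told of the revised definition before its review. A fixed pre-procedure reference also includes procedural blood loss in the drop for a later bleed, though by the same rule in both arms.

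### TIMI bleeding grades use the measured hemoglobin fall with no correction for transfused red cells, so a transfused major bleed can drop out of the major-bleeding endpoint

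*Combined protocol and SAP*

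**What the plan says.** The table of Non-CABG Surgery Related Bleeding Events Criteria gives three routes to a major bleed. Two do not depend on a blood count: symptomatic intracranial hemorrhage, and "Fatal Bleeding (bleeding that directly results in death within 7 days post procedure". The third is "clinically overt signs of hemorrhage (including imaging) associated with a drop in hemoglobin of" more than 5 g/dL, or a hematocrit drop above 15% when hemoglobin is not available. Minor bleeding is "Any clinically overt sign of hemorrhage (including imaging) that is associated with a fall in hemoglobin concentration of 3 to < 5 g/dL", or a hematocrit drop of 9 to below 15%.

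Two lower categories follow. One is "Any bleeding event that requires medical treatment, surgical treatment, or laboratory evaluation and does not meet criteria for a major or minor bleeding event". The other, the minimal category, is "A reported blood loss or bleeding event episode not meeting any of the above criteria". The table also defines a clinically significant composite of major, minor and medical-attention bleeds.

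Secondary End Point Assessments takes its first item straight from this table: "Major bleeding events as defined above using TIMI criteria". Minor bleeding is the second item, and other adverse events are the last. The Statistical analysis paragraph names major and minor bleeding as the bleeding outcomes to be compared between arms. It names neither the medical-attention category nor the composite. The Data Monitoring Committee section uses major bleeding only: "If the major bleeding events in the DOAC group occur at >15% but <30% (absolute event rate", with a stop recommendation above 30%.

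No section mentions transfusion, and none says which two hemoglobin values define the fall.

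**The concern.** Transfusion raises the measured hemoglobin. For a given true loss, a patient who is transfused before the lowest value is drawn shows a smaller fall than one who is not. Large bleeds are the ones most likely to be transfused, so the grading is least reliable for the bleeds that matter most. Because no route to a major grade uses transfusion, nothing in the major definition restores the grade.

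The Statistical analysis paragraph calls the trial a pilot of feasibility and safety, with a larger study to follow a positive signal. An undercount of major bleeding bears directly on that decision.

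Two features of the plan add to the problem. The Time and Events Schedule lists laboratory tests at baseline only, so post-procedure hemoglobin is drawn at local discretion and nothing secures a value before transfusion. The only blinding described is that of the radiologist reading the MRI. Without a written rule, sites that know the arm may differ in whether they allow for transfusion.

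**Working it through.** **Inputs from the documents.** Cut-offs: above 5 g/dL is major, 3 to below 5 g/dL is minor (bleeding criteria table). Patients analyzed: 25 per arm (Study Management and Sample Size Justification). Monitoring lines: 15% and 30% (Data Monitoring Committee).

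**Assumption, not in the documents.** One red-cell unit raises hemoglobin by c = 1.0 g/dL, range 0.5 to 1.5. All units are given before the lowest value is drawn.

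**Figure to reproduce.** None. No stated figure in the plan depends on how transfusion is handled.

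**Step 1: grade on the measured fall.** Measured fall = true fall − c × units. Example: 6 − 1.0 × 2 = 4.0 g/dL, graded minor.

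| True fall, g/dL (units) | True grade | c = 0.5 | c = 1.0 | c = 1.5 |
|---|---|---|---|---|
| 5.5 (2) | major | 4.5 minor | 3.5 minor | 2.5 neither |
| 6 (2) | major | 5.0 neither | 4.0 minor | 3.0 minor |
| 6 (4) | major | 4.0 minor | 2.0 neither | 0.0 neither |
| 7 (3) | major | 5.5 major | 4.0 minor | 2.5 neither |
| 8 (2) | major | 7.0 major | 6.0 major | 5.0 neither |
| 4 (2) | minor | 3.0 minor | 2.0 neither | 1.0 neither |
| 3.5 (1) | minor | 3.0 minor | 2.5 neither | 2.0 neither |

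*Neither* means neither major nor minor. Such a bleed falls in the medical-attention category if transfusion counts as medical treatment. A measured fall of exactly 5.0 sits in a gap between the two cut-offs.

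**Step 2: effect on an arm's rate.** One bleed is 1/25 = 4 percentage points. If the monitoring rule is read as a plain arm rate, 15% of 25 is 3.75, so 4/25 = 16% crosses the line. One downgrade gives 3/25 = 12%, which does not.

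**Step 3: direction of the bias.** Let p1 and p2 be the true major-bleed rates and f the fraction downgraded, equal in both arms. The observed difference is (1 − f)(p1 − p2), smaller than the true one. If the arm that bleeds more is also transfused more, its f is larger and the difference shrinks further. The minor count gains downgraded majors and loses downgraded minors, so its direction is not determined.

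**Step 4: how well a fixed correction works.** Adding 1 g/dL per unit gives true fall + (1 − c) × units.

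- True fall 6, 2 units: at c = 0.5, 5.0 + 2 = 7.0 (major); at c = 1.0, 4.0 + 2 = 6.0 (major); at c = 1.5, 3.0 + 2 = 5.0 (on the boundary gap).
- True fall 4.5, 2 units, c = 0.5: measured 3.5, corrected 5.5. A true minor bleed is graded major.

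The correction is exact only when c is 1.0. Otherwise it errs by (1 − c) × units, against c × units with no correction. For c from 0.5 to 1.5, the corrected error is never larger than the uncorrected one.

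**The case against.** The strongest reply is that these bleeds are not lost. A reader might infer that a transfused bleed goes unscored, or that nothing else in the plan catches it. The documents do not support that. Such a bleed needs treatment, so it meets the medical-attention category and belongs to the clinically significant composite. It is also an adverse event, and the serious-event rules may apply. What it leaves is the endpoint named for comparison and, for a major bleed, the monitoring count.

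A reader might also infer that every transfused major bleed is downgraded. That is not so. An 8 g/dL fall with 2 units stays major at 0.5 and 1.0 g/dL per unit, a lowest value drawn before transfusion is unaffected, and fatal and symptomatic intracranial bleeds are exempt. Of the five examples 5.5 (2), 6 (2), 7 (3), 4 (2) and 3.5 (1), three keep their grade at 0.5 g/dL per unit. The plan gives no transfusion frequency, so the total bias cannot be sized.

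A third tempting reading is that the safety monitoring is badly compromised. The rule is ambiguous, because it ties an absolute rate to the events in the aspirin group, and the 16% to 12% example holds only for a plain arm rate. The first review follows 50 of 52 patients, so a missed trigger could affect few enrolments. Four major bleeds in 25 (16%) would also exceed the 11% quoted in Study Rationale for all in-hospital complications after ablation for post-infarction VT.

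These limits all stand. They do not remove the central point: the rule as written grades on an uncorrected fall and can give the wrong grade.

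**Conclusion.** The concern holds in limited form. Applied as written, the criteria can move a transfused bleed with a true fall above 5 g/dL to minor or to the medical-attention category, and can take the grade from a true minor bleed. The main harm is a possible undercount of major bleeding in the final safety comparison, at 4 percentage points of an arm's rate per downgraded bleed. The bias in that comparison is toward no difference, provided the fraction downgraded is not lower in the arm that bleeds more. The minor comparison can move either way, and the effect on monitoring is small. The conclusion rests on an assumed rise of about 1 g/dL per unit (0.5 to 1.5) and on units given before the lowest value is drawn. The frequency is unknown. The point is worth correcting because safety is a stated purpose of the pilot and the remedy is cheap.

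**What to change.** In the bleeding criteria table, define the fall as baseline hemoglobin minus the lowest recorded hemoglobin, plus a prespecified amount for each red-cell unit given between the two values. An example is 1 g/dL per unit. The plan's own cut-offs pair 15 hematocrit points with 5 g/dL and 9 with 3, a ratio of 3 in both cases, so the matching hematocrit amount would be 3 points per unit. Label both amounts as assumptions, and repeat the grading at 0.5 and 1.5 g/dL as a sensitivity check.

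Apply the major and minor cut-offs to the corrected fall. Use that grade in Secondary End Point Assessments, the Statistical analysis paragraph and the Data Monitoring Committee count. Record units, times and the hemoglobin values used on the bleeding case report form. Report the clinically significant composite by arm, since it is already defined and retains the downgraded bleeds. The same edit can state which grade a fall of exactly 5 g/dL or 15% takes.

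The cost is one or two sentences and a few form fields. The per-unit amount is approximate and can occasionally grade a bleed too high, so reported rates may be slightly higher. The correction also depends on a post-procedure hemoglobin being available, which the current schedule does not ensure.
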